## **Protocol**

	Chinese:口腔舌咽肌肉功能訓練介入達文西手術後之阻塞性睡眠呼吸中止症患			
	者之成效			
Project Name	English: Efficacy of oropharyngeal myofunctional therapeutic training for			
	obstructive sleep apnea patients after transoral robotic surgery			
	NCT number: NCT04876482			
Project Director	[name]			
Research Period	Approval Date of Human Research Ethics to December 31, 2022			
Collaborating Institutions	ENT and Sleep Medicine Center, National Cheng Kung University Hospital			
Project Description	Abstract:  Obstructive sleep apnea syndrome (OSA) is caused by the complete or partial obstruction of the upper airway, leading to repeated episodes of apnea or hypoventilation during sleep, accompanied by uncoordinated chest and abdominal movements, excessive intrathoracic negative pressure, intermittent hypoxia, and decreased blood oxygen levels, potentially even sudden death. This condition is common among the middle-aged population, though its prevalence is often underestimated due to underdiagnosis. In Taiwan, the prevalence among adult men is 4%, and among women, it is 2%. The progression of the disease involves both structural and non-structural predisposing factors, making clinical symptoms varied and complex. The intermittent hypoxia associated with OSA can lead to systemic oxidative stress and a series of oxidative reactions, making it a risk factor for cardiovascular disease, which explains why cardiovascular disease is the most prevalent comorbidity in the OSA population. Other studies have found a strong correlation between daytime sleepiness and emotional states in OSA patients. Previous generational studies using drug-induced sleep endoscopy have shown that the upper airway of OSA patients is more prone to collapse during the sleep cycle, with 81% of collapses occurring behind the soft palate, 46.6% behind the tongue base, and 38.7% in the hypopharynx. In normal individuals, the driving ability of the respiratory center weakens during the sleep cycle, leading to a narrowing of the upper airway. However, OSA patients often experience insufficient muscle responsiveness of the pharyngeal			

dilators or issues with fat accumulation due to aging, particularly during the REM stage and in the supine position when muscle tone is at its lowest, making their upper airway more prone to collapse. Therefore, sleep cycles and sleep positions affect muscle tone and muscle responsiveness. Treatment options for OSA patients include sleep surgery, continuous positive airway pressure (CPAP), mandibular advancement devices, weight loss, and oropharyngeal muscle training.

#### Aim:

This project is an extension of [name] related project on the same topic from 2014 (original project approval certification number: A-ER-103-168) in the Department of Physical Therapy at National Cheng Kung University. Based on the 2014 research outcomes, this extension aims to integrate sleep surgery and multifocal interventions for neuromuscular re-education of the pharyngeal dilator muscles to explore the individuality and specificity of clinical symptoms in patients. Therefore, this study will be a controlled clinical trial.

#### **Controlled Clinical Trial:**

The study includes two aspects: clinical research and biomarker research, with the objectives outlined as follows (Figure 1):

#### **Clinical Research:**

According to clinical examination of upper airway collapse sites, multiple interventions, including surgery and neuromuscular re-education training of the pharyngeal dilator muscles, will be implemented. The treatment modalities include sleep surgery and orofacial myofunctional therapy, to investigate their clinical efficacy for OSA. Using G power analysis, with a power level set at 80% and an alpha level at 0.05, the effective sample size is estimated to be about 28 subjects per group. The planned number of subjects for the experiment is 35 per group. The experiment is divided into two groups: the experimental group and the control group. The experimental group includes (1) a post-upper airway surgery group undergoing 12 weeks of orofacial myofunctional therapy (n=35) and (2) an upper airway surgery group (n=35). The control group consists of patients undergoing self-directed weight loss, using CPAP, and waiting for mandibular advancement devices (n=35). Given that the fabrication of mandibular advancement devices takes approximately 3-4 months, relevant measurements will be taken during the waiting period. For patients attempting self-directed weight loss, the principal investigator will inquire in the clinic if they are willing to receive professional weight loss consultation. (1) If the patient is willing, they will be referred to [name] weight loss clinic in the Family Medicine Department. (2) If the patient is unwilling, they will receive self-directed weight loss education materials, and a follow-up appointment will be scheduled 6 weeks later in the ENT clinic to check the weight loss status. If weight

loss is unsatisfactory, research assistant (physical therapist [name]) will arrange bi-weekly visits to measure weight and inquire about dietary status, providing food diaries, weight control diaries from the Family Medicine Department, and exercise diaries to ensure accurate recording and monitoring of weight loss. After 12 weeks, a follow-up appointment in the ENT clinic will confirm the weight loss status. All three groups will undergo pre- and post-intervention measurements and follow-up tests in a longitudinal study design to assess the effectiveness of functional training in physical therapy for post-surgical OSA patients.

**Objective 1:** Compare the different clinical outcomes between the two experimental groups to evaluate the clinical benefits of surgery combined with orofacial myofunctional therapy.

**Objective 2:** Based on drug-induced sleep endoscopy and CT scans, divide the experimental group into three subgroups: soft palate collapse, tongue base collapse, and hypopharyngeal collapse, and compare which subgroup shows the best clinical benefits from the exercise training.

**Objective 3:** According to sleep study reports, conduct a 2x2 factorial analysis of the experimental group based on sleep cycle (REM and non-REM) and sleep position (supine and non-supine) to compare which subgroup shows the best clinical benefits from the exercise training.

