**Table 1. Detailed Sampling Description** 

MFT: Y/Surgery: Z/Control: O	Week 0	Week 6	Week 18
Basic Data Collection			
Age, Gender, and Volumetric	Y/Z/O	Y/Z/O	Y/Z/O
Parameters			
Confounding Variables			
Medical History Record	Y/Z/O	Y/Z/O	Y/Z/O
Medication Record	Y/Z/O	Y/Z/O	Y/Z/O
Craniofacial Abnormality	Y/Z/O	Y/Z/O	Y/Z/O
Examination Record			
Sleep Clinical Symptoms Record	Y/Z/O	Y/Z/O	Y/Z/O
CT	Y/Z/O		Y/Z/O
Sleep-related Assessments			
Polysomnography	Y/Z/O		Y/Z/O
Drug-induced sleep endoscopy	Y/Z/O		Y/Z/O
Mental state assessment			
HADS	Y/Z/O	Y/Z/O	Y/Z/O
Muscle function tests			
Tongue	Y/Z/O	Y/Z/O	Y/Z/O
Pharyngeal Lateral Wall Muscles	Y/Z/O	Y/Z/O	Y/Z/O
Masticatory Muscles	Y/Z/O	Y/Z/O	Y/Z/O
Others	Y/Z/O	Y/Z/O	Y/Z/O
Biomarker test	Y/Z/O	Y/Z/O	Y/Z/O

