#### **Experimental Procedures and Methods:**

#### (1) Assessment Process:

Experimental Procedures and Testing Items: The experimental steps primarily

follow standard clinical procedures, detailed as follows:

- i. Screening through the sleep clinic to determine if further sleep-related assessments are needed (current clinical procedures).
- ii. Establishing the diagnosis of obstructive sleep apnea syndrome through sleep examinations (current clinical procedures, requiring overnight sleep studies at a sleep center).
- iii. Participants agree to self-weight management, use CPAP, await the fabrication of an anti-snoring dental appliance, or undergo sleep surgery.
- iv. Recruiting clinical participants based on inclusion and exclusion criteria, providing comprehensive study information, and informing participants of their right to withdraw from the study at any time. Participants will complete the consent form and will be orally introduced to the study grouping method during the clinic visit. Participants will choose their group based on personal preference and officially enter the clinical research study.
- v. Using computed tomography (CT) and drug-induced sleep endoscope examination to understand the pre-surgical pharyngeal anatomy.
- vi. Performing tongue muscle function tests, recording the results to understand pre-intervention functional indicators (approximately half an hour).
- vii. Conducting biomarker tests to understand pre-intervention biomarker indicators.
- viii. As detailed in Table 1, measurement parameters include sleep-related assessments, mental state assessments, drug-induced sleep endoscope examination, CT scans, respiratory-related muscle function tests, and biomarker tests. Pre- and post-surgical measurements, as well as follow-up measurements, will be conducted and repeated.
- Assessment Location: NCKU Hospital Physical Therapy Center

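### Objectives 2 and 3 ask which subgroup gains most from exercise, but no planned analysis separates exercise benefit from surgical response within subgroups

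*Combined protocol and SAP*

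**What the plan says.** The Clinical Research section of the protocol defines the experimental group as two arms, surgery followed by 12 weeks of "orofacial myofunctional therapy (n=35) and (2) an upper airway surgery group (n=35"). Objective 1 compares these two arms.

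Objective 2 then sets out to "divide the experimental group into three subgroups: soft palate collapse, tongue base collapse, and hypopharyngeal collapse", using drug-induced sleep endoscopy (DISE) and CT, and to "compare which subgroup shows the best clinical benefits from the exercise training". Objective 3 will "conduct a 2x2 factorial analysis of the experimental group based on sleep cycle (REM and non-REM) and sleep position (supine and non-supine"), with the same question. The Chinese version uses the same term for the group in both objectives, so this is not a slip of translation.

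The Statistical analysis section lists baseline tests, Wilcoxon signed-rank pre/post tests, a GEE difference in differences between the three groups, and adjusted time effects for muscle strength and biomarkers. It names no collapse site, sleep stage or position, and no interaction of any of these with arm.

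Arms are self-selected. The Assessment Process states: "Participants will choose their group based on personal preference".

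**The concern.** Which subgroup benefits most from exercise is a question about how the MFT-minus-surgery difference varies between subgroups. Nothing in the plan estimates that quantity.

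- **All surgical patients pooled, arm not in the model.** Everyone had surgery, so a site difference in surgical response appears in full. Only half had exercise (35 of 70), so a true site difference in exercise benefit appears at about half its size.
- **MFT arm alone.** Every patient also had surgery and there is no comparator within the subgroup, so the two effects cannot be separated.

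Either way, a site where surgery works better could be published as the site where exercise works best.

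Two definitions are also open. Patients who collapse at several sites do not fit a three-way split, and no rule for them is visible. For Objective 3, REM/non-REM and supine/non-supine could classify patients, or could be conditions within one patient's polysomnogram (PSG). The text does not say which, and the two need different models.

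**Working it through.** **The plan's own figure.** The only sample-size statement is that "the effective sample size is estimated to be about 28 subjects per group", at 80% power and alpha 0.05, with 35 planned. Test, endpoint and effect size are not given, so 28 can only be back-solved. With two-sided alpha and the normal approximation, d = 2.80 × √(2/28) = 0.75 SD. It can be neither confirmed nor called wrong. No figure is given for Objectives 2 or 3.

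**Overlap of sites.** The abstract cites, from earlier studies, "81% of collapses occurring behind the soft palate, 46.6% behind the tongue base, and 38.7% in the hypopharynx". The sum is 81 + 46.6 + 38.7 = 166.3%. Read as patient shares, this is 1.663 sites per patient on average. If a share m has two or more sites (three at most), then 1.663 ≤ (1 − m) + 3m, so m ≥ 0.663/2 = 33.15%. If those rates carried over, that is 0.3315 × 70, or about 23 patients.

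**Misleading site differences (illustration).** Assumptions: no exercise-by-site difference; SD of change 1; a surgery-by-site difference d, for which the documents give no source; site present versus site absent; two-sided 0.05; site prevalence p = 0.81, 0.466 and 0.387. SE = √(1/(N p(1 − p))).

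Example: N = 70, p = 0.466, d = 0.3. SE = √(1/(70 × 0.249)) = 0.240; 0.3/0.240 = 1.25; rejection probability 24%.

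| Comparison | d = 0.2 | d = 0.3 | d = 0.5 |
|---|---|---|---|
| Pooled, 70 patients | 10-13% | 17-24% | 38-55% |
| Pooled, 56 patients (28 per arm) | 9-12% | 14-20% | 31-46% |
| MFT arm alone, 35 patients | 8-9% | 11-14% | 21-31% |

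Ranges run over the three sites. The nominal rate is 5%.

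**Precision of the right contrast.** For one site at a time, the arm-by-site interaction has SE = √(2/(n p(1 − p))) with n per arm. For palate with n = 35: √(2/(35 × 0.81 × 0.19)) = 0.609, and × 2.80 gives 1.71 SD. The overall MFT-versus-surgery contrast has 2.80 × √(2/35) = 0.67 SD. Only about 35 × 0.19 = 6.7 patients per arm would have no palatal collapse.

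Fitting the three sites jointly costs more. Simulated with independent sites and random arm, the detectable interactions at 80% power (palate / tongue base / hypopharynx) are:

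| | No covariates | Five assumed covariates |
|---|---|---|
| 35 per arm | 1.81 / 1.40 / 1.43 SD | 1.89 / 1.46 / 1.49 SD |
| 28 per arm | 2.06 / 1.58 / 1.62 SD | 2.18 / 1.67 / 1.71 SD |

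**Error rate of the right contrast.** In the same simulation, in change-score form with no true interaction, the uncorrected robust z-test rejects in about 7-12% of trials per term with 35 per arm and 8-14% with 28. At least one of the three terms is falsely significant in about 22% (35 per arm, no covariates) to 30% (28 per arm, five covariates). Model-based t tests give about 5% per term and about 14% for at least one of three, in line with 1 − 0.95³ = 14.3%.

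**The case against.** **The surgery-by-site differences are hypothetical.** This stands. Surgery is directed at the collapse sites, so the size and direction of any difference are unknown, and site present versus absent is not the three-way split that Objective 2 describes. The percentages show what could happen; they do not estimate a bias in this trial. At 0.2 SD the excess is modest.

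**An interaction term does not by itself make the analysis safe.** This stands too. Tested with an uncorrected sandwich z-test, it has per-term error rates similar to those of the pooled comparison at 0.2 SD. Hence the small-sample inference under the fix.

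**The payoff is limited.** With detectable differences well above 1 SD, the objectives will hardly be settled. That is a reason to report exploratory estimates with intervals. It does not justify a comparison that leaves exercise benefit and surgical response mixed.

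Some stronger readings are tempting but not supported:

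- A reader might infer that including surgery-only patients is itself the error. They are the comparator the question needs, provided arm is in the model.
- A reader might infer that the plan has no rule for multi-site patients. One can say only that none is visible: the figures, including the flow diagram to which the objectives refer, are not shown, and some pages were not available.
- A reader might infer that a third of this trial's patients collapse at several sites. The rates come from earlier studies, and the English wording gives shares of collapses. A total above 100% makes sense only if sites overlap, but the 33% bound depends on reading them as patient shares.
- A reader might take Objective 3 to be clearly patient-level. The word subgroup points that way, but factorial conditions within one PSG fit the text as well.

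**Conclusion.** The point holds on the text. Objectives 2 and 3 ask about exercise benefit in a group of which half receives no exercise, and no planned analysis contains the arm-by-subgroup contrast that would answer them. This does not depend on any assumed figure.

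The size does depend on assumptions. With surgery-by-site differences of 0.2 to 0.5 SD, the chance of a misleading site finding is 10-55% in 70 pooled patients and 8-31% in the MFT arm alone. The precision and error-rate figures further assume the cited prevalences, independent sites and unconfounded arm choice. Because patients choose their arm, the last of these is unlikely to hold without adjustment, and adjustment may not restore it. The documents give no prevalence for sleep stage or position phenotypes, so no precision is computed for Objective 3.

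The plan should be changed before analysis. Objective 1, the direct comparison of the two surgical arms, is not touched by this point.

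**What to change.** **Objective 2.** Replace the three-way split with three baseline yes/no site indicators per patient, with a stated rule for when DISE and CT disagree. In all surgical patients, add group-by-time-by-site terms, with their lower-order terms, to the planned GEE. The estimand is how the MFT-minus-surgery change differs by site.

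**Inference.** Use a bias-corrected sandwich with a t reference. For outcomes measured only at weeks 0 and 18 (PSG, CT, DISE), a change-score linear model with model-based t tests is an alternative.

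**Objective 3.** State whether stage and position are patient-level phenotypes or within-patient conditions. Then estimate the matching MFT-minus-surgery contrast: group-by-time-by-phenotype, or group-by-time-by-condition within patient.

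**Self-selection.** Adjust for a short pre-listed set, entered as covariate-by-time terms so that they act on the change: baseline OSA severity, age, gender, body-size measures, and selected items listed in Table 1 under "Confounding Variables". Age and gender need naming because Table 1 lists them under a different heading.

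**Reporting.** Describe the results as exploratory associations, give 95% CIs, state how many interactions were examined, and name no best subgroup.

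**Cost.** SAP wording and data layout only. DISE, CT and PSG are already scheduled at weeks 0 and 18 and the confounders are already recorded. If the named software lacks the small-sample correction, another package is needed for that step. The downside is low precision: the palate term will be close to uninformative, and residual confounding from patient choice remains.

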#### **Statistical analysis:**

Continuous variables are presented as mean and standard deviation (SD), whereas categorical variable is presented as numbers and percentages. Kolmogorov-Smirnov test was used to analyze the normal distribution of the variables. Due to the non-normal distribution, Kruskal–Wallis test and Fisher's exact test was used for continuous and categorical data to compare baseline characteristics among the study groups. Besides, the Wilcoxon signed-rank test was used to compare the pre- and post-differences in demographic characteristics, questionnaire, sleep parameters and the data of CT image. Linear regression model with generalized estimating equations (GEE) was used to estimate (1) the difference in differences and the corresponding 95% confidence intervals (CIs) of pre-treatment to post-treatment changes between the 3 groups and (2) multivariate adjusted effects of time in muscle strengths and biomarkers. The working correlation matrix was defined as unstructured. P < .05 was defined as statistically significant. All the statistical analyses were conducted by using SPSS 17.0.

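### Objectives 2 and 3 ask which subgroup gains most from exercise training, but no test is planned of whether the training effect differs between subgroups

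*Combined protocol and SAP*

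**What the plan says.** The sample size paragraph under Clinical Research begins "Using G power analysis", continues "with a power level set at 80% and an alpha level at 0.05", and concludes that "the effective sample size is estimated to be about 28 subjects per group". It then adds: "The planned number of subjects for the experiment is 35 per group". No effect size, SD, outcome, test or sidedness is given. The groups are surgery plus 12 weeks of myofunctional therapy (MFT), surgery alone, and a non-surgical control.

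Objective 1 compares the two surgical arms. Objective 2 divides the surgical patients into three collapse-site subgroups and ends "hypopharyngeal collapse, and compare which subgroup shows the best clinical benefits from the exercise training". Objective 3 forms a 2x2 from sleep stage and "sleep position (supine and non-supine) to compare which subgroup shows the best clinical benefits from the exercise training". The Chinese text asks the same ranking question in both objectives.

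The Statistical analysis section plans a GEE difference in differences between the three treatment groups, with "P < .05 was defined as statistically significant". It mentions no subgroup term, interaction test, multiplicity control or exploratory status. The abstract gives collapse frequencies from earlier work of 81% (soft palate), 46.6% (tongue base) and 38.7% (hypopharynx).

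**The concern.** Asking which subgroup is best presupposes that the subgroups differ. The prior question is whether the surgery+MFT minus surgery effect varies between subgroups at all, and nothing in the analysis section addresses it. Without that step, the natural way to answer is to look for the largest estimate. One estimate is always largest, so a subgroup is named even under equal benefit. An estimate picked for being largest is also, on average, too large.

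The cells are small compared with the only sample size the plan gives. A report could therefore name a collapse site or sleep pattern as the one that responds to training when the ordering is largely chance, and attach an inflated benefit to it.

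**Working it through.** **The plan's own figure.** The 28 per group cannot be reproduced, because no effect size or test is stated. Working backwards at alpha 0.05 and 80% power:
- two-sided two-sample t test: d = 0.76
- normal approximation: (1.960 + 0.842) × √(2/28) = 0.75
- one-sided t test: d = 0.67

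I use d = 0.76 only as a scale. The planned 35 is consistent with 28/0.80 = 35, but no dropout rate is stated. I therefore carry both 28 and 35.

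**Cell sizes per arm, even and exclusive split (assumption).**
- Three sites: 35/3 = 11.7; 28/3 = 9.3.
- Four cells: 35/4 = 8.75; 28/4 = 7.0.

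**Overstatement of the top subgroup when true effects are equal.** In SD units, each subgroup's training effect has SE = √(2/n). The expected maximum of k independent standard normals is 0.85 for k = 3 and 1.03 for k = 4. Their product is the mean overstatement.

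| Split | n per arm | SE | Mean overstatement (SD) | Power in cell at d = 0.76 |
|---|---|---|---|---|
| 3 sites, 35 | 11.7 | 0.414 | 0.35 | 42% |
| 3 sites, 28 | 9.3 | 0.463 | 0.39 | 34% |
| 2x2, 35 | 8.75 | 0.478 | 0.49 | 32% |
| 2x2, 28 | 7.0 | 0.535 | 0.55 | 26% |

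The effect detectable with 80% power inside a cell rises from 0.76 SD to between 1.22 and 1.63 SD.

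**How often ranking finds the right subgroup.** Suppose one subgroup has 0.76 SD and the others half of it (0.38 SD). In simulation the largest estimate is the right one 58% to 61% of the time with three subgroups (chance 33%) and 46% to 49% with four (chance 25%).

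**Sensitivity to the split in Objective 2.** The abstract's frequencies sum to 81 + 46.6 + 38.7 = 166.3%, so patients can collapse at more than one site.
- Exclusive cells in those proportions: about 17/10/8 per arm at 35 and 14/8/7 at 28. The overstatement is 0.37 to 0.41 SD.
- Overlapping subgroups: about 28/16/14 per arm at 35 and 23/13/11 at 28. Simulating independent membership, the overstatement is about 0.20 SD at 35 and 0.23 SD at 28.

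**Power of an overall interaction test.** I used a chi-square on k − 1 df with noncentrality Σ(effect − mean effect)²/SE², even split. One subgroup has 0.76 SD.
- Others at half that: 0.38² × (k − 1)/k divided by SE² gives noncentrality of about 0.4 to 0.6. Power is about 9% to 10% for three subgroups and 7% to 8% for four.
- Others at zero: 21% to 25% and 15% to 18%.

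**The case against.** The strongest reply is that the plan contains no selection rule. The objectives pose a research question, and comparing subgroups ordinarily means tests or intervals. Objective 3 names a factorial analysis, which can return no difference. This stands in part. A reader might infer that the plan commits to declaring the largest estimate the winner, and it does not say so. The overstatement describes ranking, not a written procedure. But the analysis section supplies no alternative to ranking, and a factorial analysis of stage and position does not test variation in the training effect unless arm is crossed with them.

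Second, the even, exclusive split is an assumption that the plan's own collapse frequencies do not favour. That stands, and overlap cuts the three-site figure to about 0.20 to 0.23 SD.

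Third, REM/non-REM and supine/non-supine may be conditions within one patient's night. The text speaks of subgroups, so the patient reading is natural, but the classification is undefined. On the within-patient reading the 7 to 9 per cell do not apply.

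Fourth, a reader might infer that the plan claims 80% power for the subgroups, because the sample size sentence precedes all three objectives without limitation. The sentences around it define the groups as treatment arms, so that reading is not supported.

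Fifth, the Expected Results section hopes to guide practice, but that remark is about the controlled, interdisciplinary design. It does not show that a subgroup ranking would direct referral.

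**Conclusion.** The concern holds as a gap between objectives and analysis: two objectives ask for a best subgroup, and no planned test establishes that subgroups differ. Answered by ranking with equal true effects, the top subgroup would be overstated on average by about 0.35 to 0.39 SD (three sites) or 0.49 to 0.55 SD (2x2 as patient subgroups) under an even, exclusive split. With overlapping, independent sites the three-site figure is about 0.20 to 0.23 SD. These overstatement figures do not depend on any effect size. The within-cell power of 26% to 42% does: it rests on the back-calculated d = 0.76 and a two-sided t test.

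A reader might also infer that shrinkage estimation is needed to repair this. It is not essential and is not a full cure. If the heterogeneity test is passed by chance under equal effects, a shrunken winner is still too large by about 0.58 to 0.76 SD. Objective 1 is unaffected by this point.

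**What to change.** In Objectives 2 and 3, replace the ranking question with wording such as: *estimate the training effect (surgery+MFT minus surgery) in each subgroup with a 95% CI, and test arm-by-subgroup interaction in the GEE model, with one overall test per objective.* Add the matching term to the Statistical analysis section. State whether collapse sites are exclusive or may overlap, and whether the 2x2 classifies patients or conditions within a patient, since the form of the test depends on it.

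Report all subgroups together and call none best on ranking alone. Treat any difference found as exploratory and needing confirmation, because an estimate selected after a significant test is still too large. In the sample size paragraph, say that 28 per group and 80% power refer to whole treatment arms. Shrinkage may be added but is optional.

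The cost is wording and a small amount of analysis, with no extra patients, visits or procedures. The downside is that the plan promises less from the subgroups. The interaction test will also usually miss a real difference: its power is about 7% to 10% if one subgroup benefits twice as much as the rest, on the scale and even split used above. A non-significant result must therefore not be read as equal benefit.
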